During the second month of the study, we will establish the participant's baseline adherence to daily asthma controller medication and need for rescue short-acting beta-agonist. Thus, the study team, participant and family will be blinded to this baseline data collection.

At the time of the initial self-management session month 3½, the Propeller Health platform will be turned on and data on the participant's baseline adherence to daily asthma controller medication and need for rescue short-acting beta-agonist shared with the study team, participant, and family. The participant and parent/guardian will receive the participant's inhaler usage for the current and preceding week. They will also receive smartphone alerts from the Propeller Health app reminding them to use their controller inhalers and alerts when they use rescue medication prompting them to select their symptoms and triggers based on a pre-populated list.

Propeller caps will be collected at the end of the study.

CCHMC Visit 2 (V2): The study coordinator will conduct this visit at CCHMC. The participant will complete asthma questionnaires, an Asthma Control Test (ACT), and the TreatSmart program on a CCHMC secured laptop. TreatSmart will determine if participant's treatment dose should remain the same or be changed based on their level of control. Asthma education will be reinforced. These procedures are similar to those outlined above in the baseline medical visit.

The study team will also review the results of the biomarker assays (genetic and environmental) and discuss the results with the family. One of the pulmonary or allergy specialist investigators ([name], [name], [name], [name], [name],

pulmonary or allergy fellow or asthma research or pulmonary nurse practitioner) will perform a physical exam, review PFT report, review the TreatSmart program visit

summary and treatment recommendations, and make a personalized plan of medications and a revised home environmental trigger remediation plan based on the environment and genetic biomarker assays and self-management assessments. The visit summary, asthma medication and home trigger remediation plan recommendations and asthma action plan from the medical visit will be physically given to the participant and family. These documents in the form of a letter will be sent to the primary care provider by the study team.

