Adherence data from the Propeller Health monitoring system will be available to families beginning at the time of the initial self-management visit via the Propeller app. This data will also be reviewed with the participant by the adherence specialist during adherence visits and one of the study staff during the second medical visit. The adherence specialist will also provide customized supportive text messages originating from the CCHMC email system to the participant's smartphone or iPad. Text messages will not include personal health information, but instead will provide support and reminders related to adherence (e.g., Hello, remember to use your inhaler today!, Don't forget to put a reminder in your locker, Have you been using your monitoring log?).

Participants with 51-79% adherence rates during the first two months will receive a text messaging only intervention, with text messages being sent from the CCHMC email system to the participant's smart phone or iPad to aid with adherence, problem-solving and motivation. Similar to the previously mentioned intervention, text messages will provide support and reminders related to adherence (e.g., Hello, remember to use your inhaler today!, Don't forget to put a reminder in your locker, Have you been using your monitoring log?).

Participants with ≥ 80% adherence rates during the first two months will not receive any adherence intervention.

Phone Calls: Up to ten scheduled phone calls will be made during the study to the family smartphone or home telephone to complete the Asthma Control Test, the Treatsmart program, and the concomitant medication form to document any changes to medications since the last phone call or study visit. These phone calls will collect our primary outcomes after the intervention is delivered and also serve as a point of contact to keep the families engaged in the study. During the call, the family will be asked to upload their data from the Propeller Adherence app from their smartphone or iPad. One of the pulmonary or allergy specialist investigators ([name], [name], [name], [name], [name]) will review the TreatSmart program data summary, any new medications that were started, and treatment recommendations. If a medication change is needed, a sick visit will be scheduled with a study investigator at one of their upcoming clinics. If a monthly phone call is missed or unable to be completed during a monthly phone call visit window, an

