The participant's asthma action plan contains advice for handling increased or severe asthma exacerbations and when to call the study team or when the family should take the child for evaluation to the school nurse, school-based health clinic, community primary care provider, or a local urgent care or emergency department. This data will be collected at the patients next study visit if the family didn't call the study team. The school nurse (if the school nurse referred participant to the study) or PCP will also be encouraged to contact the study team if additional advice on the asthma treatment of a study participant is desired. The study team can then determine if a sick visit is needed.

In addition, the CCHMC study team will receive a Propeller Health a weekly report of participants that have not taken their daily controller medication in the last 7 days, have changed their asthma symptoms control level, or have experienced a 200% increase in their rescue medication use in the past 24 hrs. The study team will communicate with the participant's family to gather more information on the severity of their asthma symptoms using the Phone Call Exacerbation Form. If the participant is experiencing severe symptoms, they will be encouraged to be urgently evaluated by the school nurse, school-based health clinic, community primary care provider, or a local urgent care or emergency department.

Other:

Community Engagement: A goal of this initiative is to identify as many DTT patients as possible from community sites. We will accomplish this by capitalizing on our existing partnership with CPS and CHD by providing them an enhanced tool for the school ACT screening program. This program currently screens over 80% of the asthmatics attending CPS schools; we will offer the screening tool to FQHC and CHD practices as well. The identified patients will be invited to participate and all will be

identified to school nurses and their PCMHs. For those who choose not to participate in the program, we will collect reason for non-participation, share it with our community

partners, and use the data to improve our program and identify alternative interventions for non-participants. Referral to existing programs, a CCHMC specialty asthma clinic, or a school-based health clinic will be offered. In addition, we will provide clinical support via telephone or telemedicine consultation for the school nurses,

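### The weekly Propeller report to the study team looks back only 24 hours for a jump in rescue-inhaler use, so as worded a jump on any of the other six days is not listed under that trigger.

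*Combined protocol and SAP*

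**What the plan says.** The rule is in section 8 (Study Procedures), under Asthma Exacerbations during Study Follow-up. The team receives "a weekly report of participants that have not taken their daily controller medication in the last 7 days". The same sentence adds two further triggers: participants who "have changed their asthma symptoms control level", and those who have "experienced a 200% increase in their rescue medication use in the past 24 hrs".

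Being listed has a consequence. The team contacts the family, records severity on a dedicated form, and advises urgent evaluation if symptoms are severe.

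Three other parts of section 8 bear on the point:

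- **Propeller subsection.** In the second month the study establishes each child's "baseline adherence to daily asthma controller medication and need for rescue short-acting beta-agonist". Team and family are blinded to these data, which are shared at month 3½. From then on the participant and family also receive "alerts when they use rescue medication prompting them to select their symptoms and triggers".
- **Phone Calls subsection.** At the scheduled calls "the family will be asked to upload their data from the Propeller Adherence app from their smartphone or iPad".
- **Exacerbations subsection, before the report is introduced.** Each family has an asthma action plan that says when to call the team or seek care.

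**The concern.** A report issued once a week should look back over the week since the last one. The controller trigger does. The rescue trigger, in the same sentence, looks back one day. Followed literally, a child whose rescue use jumped early in the week and then settled would not appear under that trigger when the report is issued.

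The study enrols children with uncontrolled moderate or severe persistent asthma, and a sharp rise in rescue use is a natural warning sign in them. The listing is what prompts the team to call without waiting for the family to do so. The documents describe no daily or same-day rescue-use alert to the team that would make up for a narrow window. What is at stake is how well one safety-follow-up prompt works. The primary outcome and its analysis are not involved.

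**Working it through.** The plan states no figure for this rule, so there is nothing to reproduce. The check compares the look-back window with the reporting interval.

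**Inputs, all from section 8, Asthma Exacerbations during Study Follow-up**

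- Reporting interval: weekly, 7 × 24 h = 168 h.
- Controller look-back: 7 days = 168 h.
- Rescue look-back: 24 h.
- Control-level trigger: no look-back stated.

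**Step 1. Coverage = look-back ÷ reporting interval**

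| Trigger and reading | Covered | Not covered |
|---|---|---|
| Controller, as written | 168/168 = 100% | 0% |
| Rescue, literal reading | 24/168 = 14.3% | 144/168 = 85.7% (six of seven days) |
| Rescue, rule applied daily and the week's hits listed | 168/168 = 100% | 0% |
| Rescue, any 24-hour period since the last report | 168/168 = 100% | 0% |

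The second and third rows are both possible readings of the current text. The result therefore runs from no gap to six days in seven, depending on how the vendor has set up the report.

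**Step 2. Delay after widening the window**

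With a report at the end of day 7, an event on day k is notified 7 − k days later. For k = 1 that is 6 days; for k = 7 it is 0 days. Any delay before the sensor data reach the platform is added. The documents say that families are asked to upload at the scheduled calls, but not how often data otherwise reach the report.

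**Step 3. The comparator (secondary)**

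A 200% increase means (new − reference)/reference = 2, so new = 3 × reference. The sentence does not say what the reference is. With a reference of zero the ratio is undefined. The month-2 rescue need is the one baseline the plan collects, but nothing links it to this trigger.

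**Step 4. What cannot be computed**

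The documents give no rescue-use rates and no expected frequency of such jumps. The percentages in Step 1 are shares of time covered. They cannot be turned into numbers of children or events.

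**The case against.** The strongest reply is that the 24 hours may define the alert itself, a one-day spike, with the weekly report listing everyone who tripped it at any time that week. On that reading coverage is complete. The text permits it, and the deciding fact is a vendor setting outside the documents. This stands as a limit on the size of the point. It does not remove the point, because the sentence as written can also be set up the narrow way.

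A second reply is that the report is a backup. The protocol introduces it as an addition to the asthma action plan. The control-level trigger carries no 24-hour limit and may catch a sustained deterioration. Families get app alerts from month 3½, the scheduled calls include investigator review, and the referring school nurse and primary care provider are encouraged to contact the team. This stands, and it is why the severity is low. These routes do not do the same job, however: the action plan depends on the family acting, the app alerts go to the family, and the calls are roughly monthly.

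A reader might infer that the team misses 86% of deteriorations, or that children are left unmonitored between calls. The documents support neither. The 86% is a share of hours on one reading, and the other routes remain open. Inhaler use is also recorded on the web platform, and nothing says that the weekly report is the team's only view of it.

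A reader might also take the month-2 baseline as the obvious comparator. It is blinded until month 3½, so it could serve only from then. It also comes before the personalized plan made at V2, so it may not represent usual use later in the year.

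**Conclusion.** The point holds in a narrow form. A weekly report is paired with a one-day look-back for rescue use, so as written a 200% rise confined to any of the other six days is not listed under that trigger. The size is 144 of 168 hours uncovered on the literal reading, and none if the platform already evaluates each day and lists the week's hits. The documents do not settle which.

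The conclusion assumes that the report is issued once every seven days, as stated, and that no same-day rescue-use alert reaches the team. The documents describe none, which is weaker than showing that none exists.

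Severity is low. The flag is supplementary, the number of children affected is unknown, and neither the CASI outcome nor its analysis changes. The unstated comparator is a real gap in detail on either reading, but it is a clarification and secondary to the window.

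**What to change.** Reword the criterion in section 8, Asthma Exacerbations during Study Follow-up, as: a 200% increase in rescue medication use in any 24-hour period since the last weekly report. Then confirm with the vendor that the report is set this way. If it already is, only the wording changes.

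As a secondary clarification, name what the 200% is measured against and say how a reference of zero is handled. If the month-2 baseline is chosen, another reference is needed before month 3½.

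The cost is one sentence of protocol text, one vendor check and somewhat more follow-up calls among the 30-50 children. The gain is limited by timing: notice still comes 0 to 6 days after the event, plus any sync delay, so the flag continues to supplement the asthma action plan and cannot replace it.

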4. STUDY DESIGN

We will conduct study visits in the Schubert clinic to determine and quantify known molecular, genetic, genomic, epigenetics, immunologic, and exposure biomarkers that will help elucidate molecular disease endotype within the DTT phenotype (Figure 1). This information will be used along with clinical, psychosocial, and adherence data to develop

a personalized treatment plan. We will track disease outcome metrics including exacerbations, symptom-free days, and a validated asthma composite control score to determine the effectiveness of this personalized approach (summarized in Figure 1).

A number of interventions will be incorporated based on information collected on questionnaires on personal and family medical history, history of environmental exposures, previous and current residential and school addresses, depression, anxiety, dietary intake, adherence, medical literacy, and perceived quality of life, medical visits, use of a commercially available inhaler cap monitoring sensor, a mobile software management platform that tracks adherence of asthma medications, mobile based telehealth adherence problem-solving interventions, biomarker assays and home trigger assessment and remediation.

This proposal is funded through a CCHMC ARC award.

5. DURATION:

Duration for the participants will be 12 months. We will continue to follow asthma outcomes via the patient's medical record for an additional 12 months. Participants will be enrolled in the study during the 24 months of the project. If additional funds are awarded, the enrollment period may be extended to a third funding year. Data analysis will be performed 6 months after the last participant completes the project.

6. SELECTION & RECRUITMENT OF PARTICIPANTS:

A. Number of participants

Patient Population: 30-50 6-17 year old children with uncontrolled moderate-severe persistent asthma without significant chronic disease other than allergic disorders.

B. Inclusion/Exclusion criteria

Inclusion

- age 6-17 years; history of provider-diagnosed asthma;
- Meets one of the following definition for NAEPP guidelines uncontrolled moderate persistent asthma or severe persistent asthma in the past 12 months:
 - NAEPP step 3-4 with one of the following criteria in the past 12 months:
 - two ACT scores <20
 - ≥ 1 UC/ED visit or hospitalization for asthma
 - ≥ 2 prednisone bursts
 - NAEPP step 5-6

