Study Termination. During each medical visit, the number of severe asthma exacerbations [treated with systemic steroids; hospitalizations for asthma; PICU admission, intubation or hypoxic seizure due to asthma] since the start of the study will be determined. If the participant has ≥ 4 severe asthma exacerbations or > 2 asthma-related hospitalizations during the study, study participation will be ended. The procedures for the end of study will also be followed with the recommendation of referral to the CCHMC Difficult-to-Treat Asthma Clinic.

If patient/patient's family are not able to be reached for multiple weeks throughout the study, a MOP has been put into place as a plan for re-gaining communication. Please refer to the *Study Discontinuation MOP* for more details regarding this communication plan. If plan has been carried out and study staff are still unable to reach patient/patient's family, the participant will be discontinued from the study. In the event that a participant is discontinued from the study, a letter will be mailed to the patient/patient's family with instructions to resume asthma care from the physician who was treating them prior to the study.

If a participant was loaned a device, an iPad or Cradlepoint to complete the Telehealth portion of this study, these devices will be collected upon study termination/completion. If

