a participant completes all study activities, this equipment will be collected at the final home visit (H2) or once the self-management visits are completed coordinators will schedule to come pick up the equipment from the family's home. If a participant is discontinued from the study early due to lost to follow-up, study staff will follow the *Study Discontinuation MOP* in order to collect the loaned iPad and Cradlepoint. The actions taken will include: phone calls, text messages, emails, letters mailed to the home, and home visits. If the equipment is not recovered, a certified letter will be sent to the home with instructions to return the iPad and Cradlepoint with a copy of the *Telehealth Agreement Form* that was signed at the first Home Visit (H1). Per the signed *Telehealth Agreement Form*, families are responsible for notifying CCHMC if the iPad is lost or stolen. "iPads that are lost or stolen will be reported to the CCHMC Protective Services Department and to the appropriate Police Department". If the equipment is not returned after all steps in the *Study Discontinuation MOP* have been followed, the Telehealth department at CCHMC will be notified that the equipment was not recovered.

9. DATA ANALYSIS/METHODS:

Study Outcomes:

The adolescent's asthma outcomes and adherence will be measured at baseline and during the clinical visits or study telephone calls once a month for a total of 12 months. Outcomes will be measured during the monthly medical visits using a computerized TreatSmart program based on the NAEPP asthma guidelines which was adapted by the CCHMC Asthma Center database team from the Inner City Asthma Coalition (Appendix C), ACT scores, and Propeller Health web-based inhaler cap monitoring sensor and mobile software management platform (Appendix B).

Primary Outcome:

Composite asthma severity index (CASI) score collected monthly during phone calls, home visits, and clinic visits over 1 year. The CASI is a severity score of symptom burden, exacerbations, healthcare utilization, lung function and dose of inhaled corticosteroids. This score will be collected and captured by the TreatSmart program.

Secondary Outcomes:

We will analyze the following outcomes: ACT score over past 4 weeks; rescue medication use, oral-steroid requiring exacerbations; healthcare utilization, lung function, dose of inhaled corticosteroids, and adherence of controller medication.

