These asthma related outcomes are commonly reported in both the adult and pediatric asthma literature and are endorsed by national asthma guidelines and the National Institutes of Health (NIH) asthma-outcome conference.

Data Analysis

We will use descriptive statistics to characterize the sample demographics. A descriptive analysis with calculation of means, medians, and standard deviations will be performed for each continuous measure; categorical measures will be examined with percentages. If necessary, we will log-transform non-normal data; however if a normal distribution cannot be attained we will use nonparametric statistics. We will use paired t-tests to evaluate the null hypothesis that there was no change in the primary outcome (CASI score) while participants are blinded to data collected by the Propeller medication sensor in the first month of participation. Nonparametric methods will be used if the assumptions for paired t-tests are violated. The primary analyses will test whether this interventional program improves CASI scores (from completion of the first month to study exit). Linear mixed effects models with a random effect for subject assessed changes in primary asthma endpoints each month across the 1 year study or upon exit. Participants with one or more observations will be included in the analysis. All statistical analyses will be implemented in SAS 9.3 (SAS Institute, Cary, NC) and use a significance level of 0.05. Potential confounders identified from the literature, such as age, gender, season of enrollment, severity of asthma at baseline, smoke exposure, environmental exposures and atopic status will be adjusted in the analyses. The REML model used for these analyses requires that any missing data are “missing at random” (MAR) to yield valid estimates. To account for the presence of possible non-ignorable missing data, pattern- mixture modeling will be applied for these analyses.

The secondary analyses will look at the ACT score, rescue medication use, oral-steroid requiring exacerbations, healthcare utilization, lung function, dose of inhaled corticosteroids, and adherence of controller medication. Linear mixed-effect models will be used to compare the continuous outcomes such as exacerbations. Generalized linear mixed effect models will be used to compare the discrete outcomes such as health system utilization, both accounting for repeated measurement over time while adjusting for confounders.

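### Children are taken off study because of the outcomes being measured, with no outcome collection provided afterwards, so descriptive event rates and the utilization model can show a fall that is not real

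*Combined protocol and SAP*

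**What the plan says.** Section 8 (Study Termination) sets the rule: at four or more severe exacerbations, or more than two "asthma-related hospitalizations during the study, study participation will be ended". It adds that "The procedures for the end of study will also be followed", with a recommended referral. It mentions no monthly call or other outcome contact after that.

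The count is taken as follows: "During each medical visit, the number of severe asthma exacerbations" since the start is determined. In Appendix A, the history and physical falls at V1, V2 (about month 3) and the optional V3 (month 12); sick visits are added as needed. Section 9, however, says "Outcomes will be measured during the monthly medical visits", although most of those contacts are phone calls.

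Section 5 plans to follow asthma outcomes through the "medical record for an additional 12 months", after 12 months of participation. It neither includes nor excludes children who were stopped, and Section 9 does not use these data.

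In Section 9, oral-steroid exacerbations and healthcare utilization are secondary outcomes and both feed the primary CASI score. The primary test runs "from completion of the first month to study exit". For the secondary outcomes, "Linear mixed-effect models will be used to compare the continuous outcomes such as exacerbations", and utilization gets a generalized linear mixed model (GLMM). Anyone with at least one observation is included. Pattern-mixture modeling is named in the primary-analysis paragraph and not repeated for the secondary outcomes.

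**The concern.** The rule removes the children with the most events and then stops counting their events. Those who remain have lower underlying rates, so an average over children still observed drifts down through the year whether or not the program works. There is no control group in which the same drift would show. Dividing by observed child-time does not cure it, because the high-rate children leave the later person-time.

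What is at stake is an apparent improvement in exacerbations and utilization that comes from who is left. It grows with the severity of the enrolled population, which is the population this pilot wants to study.

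**Working it through.** **Inputs.** From the documents: the two thresholds, 12 months on study, 30 children, and the planned models. Assumed: 2–3 severe exacerbations per child-year (also 1), varying between children as a gamma distribution with shape *k* = 1 or 2. The only anchor for the rate is one of several alternative entry criteria, two or more prednisone bursts in the past year. The plan states no figure to reproduce. All results below assume no intervention effect.

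**How many are stopped.** With mean rate μ per year, the count by time *t* is negative binomial with mean *m* = μ*t*. With a monthly check, a child is stopped before month 12 if the count after 11 months is at least 4 (exacerbation criterion only).

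- *k* = 1: P(N ≥ 4) = [*m*/(*m*+1)]⁴. At μ = 2, *m* = 2 × 11/12 = 1.833, giving 0.647⁴ = 0.175, or 5.3 of 30. At μ = 3, *m* = 2.75, giving 0.733⁴ = 0.289, or 8.7 of 30.
- *k* = 2: P(N ≥ 4) = 1 − p²(1 + 2q + 3q² + 4q³), with q = *m*/(*m*+2) and p = 1 − q. At μ = 2, q = 0.478 gives 0.16 (4.8 of 30). At μ = 3, q = 0.579 gives 0.30 (9.0 of 30).

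**If the count is checked only at V2 (month 3).** For *k* = 1, *m* = 0.5 gives (0.5/1.5)⁴ = 0.012, and *m* = 0.75 gives (0.75/1.75)⁴ = 0.034. For *k* = 2, simulation gives 0.7% and 2.1%. At most about one child in 30 is stopped.

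**Why the remaining rate is lower.** Take *k* = 1, μ = 2, monthly check. Among children with 0–3 events by month 11, the mean count is 0.98. Their expected rate is (*k* + 0.98)/(*k*/μ + 11/12) = 1.98/1.417 = 1.40 per year against a true 2.00, a ratio of 0.70 (simulated: 0.71). With no variation between children the ratio is 1.00.

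**Simulated results, months 7–12 against months 1–6, monthly check**

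| Quantity | 2 per year | 3 per year |
|---|---|---|
| Raw exacerbation rate per observed child-month | −10% to −19% | −18% to −29% |
| Utilization GLMM, ratio | 0.93–0.96 | 0.87–0.91 |

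A random-effect count model for exacerbations gave ratios of 0.997–1.004 in the same simulations.

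At 1 per year and *k* = 2, about 4% of children are stopped and the raw rate falls 2–3%.

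**Checks at sick visits.** If the count is checked at month 3 and in half of the months with an exacerbation (*k* = 2), 11% and 22% are stopped at 2 and 3 per year, and raw rates fall about 7% and 12%. If it is checked in only a quarter of those months, rates fall 4% and 8%. Repeat runs differ by about a point. Monthly and half-of-months checking together give about 6–29% for raw rates and about 3–13% for the utilization GLMM.

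**Why utilization differs from exacerbations.** For exacerbations, stopping depends on earlier observed values of nearly the same outcome, so a likelihood model with a subject effect treats the dropout as missing at random. The utilization model does not contain the exacerbation count that mainly triggers the stop, so that protection is lost. With utilization set at 30–70% of exacerbations, and 30% of those hospitalized, the fitted month-12/month-1 ratio was 0.80–0.92 at 2 per year and 0.69–0.93 at 3. The midpoints of the two half-years are 6 months apart on an 11-month span, so raising these to the power 6/11 puts them on the half-year scale: 0.89–0.96 and 0.82–0.96.

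**Full collection.** When counts are kept to month 12 whatever the stopping status, the month-12/month-1 ratio is 1.00 in every scenario.

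**The case against.** A reader might infer that exacerbation results in general fall over the year with no effect. Under the planned models they do not. The linear mixed model fitted a change of +4% to +9% in large samples. At 30 children it showed a significant decline in 0.4% (2 per year) and 2.0% (3 per year) of 250 runs, against 7.6% and 26.4% for a Poisson model with no subject effect. The monthly CASI mixed model was also sound: a month-12 contrast of +0.27 against a true +0.26. This part of the objection stands. It does not cover the planned descriptive means, or the fallback to nonparametric statistics if normality cannot be reached, which is plausible for monthly counts that are mostly zero.

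A reader might also infer a bias towards benefit in the CASI change to study exit. In an illustrative run that change was +0.38 against a true +0.26. Higher CASI is worse, so this points towards harm, and 0.12/2.4 = 0.05 SD is trivial. Section 9 also models CASI monthly, so a last-value contrast is only one reading.

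Nor do the documents say that all outcome collection ends: the record follow-up in Section 5 could hold these events. What remains is that it is described as additional to the 12 months, is not tied to stopped children, and has no place in the analysis.

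Finally, a strict reading of Section 8 puts the check at V2 and the optional V3, where the effect is negligible. Sick visits and the monthly wording in Section 9 leave more frequent checks open. Pattern-mixture modeling could help, but it is not extended to these outcomes, and with about 5 stopped children it would rest on assumptions in place of data that can be collected.

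**Conclusion.** The point holds in a limited form. Exit is driven by the outcomes under study, no later outcome contact is provided, and there is no control arm. If the rule is applied monthly or in about half of exacerbation months, at an assumed 2–3 exacerbations per year, descriptive or marginal rates fall about 6–29% with no effect, and the separate utilization GLMM falls about 3–13%. The latter reaches about 18% if only 30% of exacerbations lead to utilization, at 3 per year with *k* = 1.

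The exacerbation mixed model and the monthly CASI model are not materially affected. With a V2-only check nothing of consequence happens. These sizes rest on rates, between-child variation and a checking frequency that the documents do not settle. Because the remedy is cheap and uses a resource already planned, the change is worth making.

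**What to change.** Leave the stopping rule as it is.

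- **Section 8:** separate the end of the intervention from the end of data collection. For every enrolled child, including those stopped, abstract steroid courses, ED and urgent care visits and hospitalizations from the medical record to month 12 after V1, by stating that the Section 5 record follow-up covers this period. If the family agrees, continue the monthly CASI/ACT call to month 12.
- **Section 9:** analyse exacerbations and utilization on the full 12-month denominator, and extend the missing-data sensitivity analysis to these secondary outcomes.
- **Sections 8 and 9:** reconcile the wording on medical visits so that it is clear when the count is determined.

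The cost is a few sentences, plus record abstraction and some calls for about 5 of 30 children at 2 exacerbations per year with a monthly check (about 9 at 3 per year, at most about 1 with a V2-only check). The downside is that outcomes after stopping reflect usual care, and the record may miss care given elsewhere. The analysis should say so.
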